Potential benefits of the proposed research. Prostate cancer is the most common cancer in US men along with the increasing trend toward obesity in the general population. The development of dietary approach to improve outcomes from the surgical treatment of prostate cancer and to better understand how weight control impacts the immune system and inflammatory state will improve the quality of life for cancer survivors. The approach will meet the pressing need to identify weight control interventions for cancer survivors that may improve long-term prognosis and survival. Given the minimal risk to subjects and the potential gain from the study, the risks are considered reasonable.

Adverse event reporting:

Participants will be instructed to report any new or worsening medical condition to their coach or on their weekly self-monitoring logs. Adverse events may be obtained from medical updates taken at baseline, 1 week prior to RP, and 6 months after PCa surgery, weekly participant logs, or spontaneous reports from any source. For all adverse events, an Adverse Event Record Form will be completed that includes a description of the event, a classification of the seriousness, an evaluation of the potential relationship to the intervention, and an assessment of need for change in the informed consent or study activities. Adverse events will be reviewed weekly by the PI and monthly by the study team. Any serious adverse event (SAE) will be investigated immediately and assessed for relevance to the study by the study physicians and

medical monitor. All related and unexpected SAEs will be reported to the KUMC IRB/HSC within 48 hours of the report of the SAE.

Safety Monitoring/Medical Monitor. Serious side effects or other problems during this study will be reported to PI, [name], Co-I, [name], and Medical Monitor, [name], MD.

Medical Monitor: *[name], MD*
Assistant Professor of Urology
[contact]

An external Medical Monitor will evaluate adverse effects. [name] is a qualified physician, not associated with this particular protocol and not under the supervision of anyone on the research team. [name] will monitor data collection and safety by reviewing the research protocol with emphasis on data integrity and patient safety issues. [name] will monitor any adverse events during the course of the study, make decisions about the continuance of subjects, communicate with the investigators and physicians about adverse events, and assess the responsiveness of corrective actions.

More specifically, the medical monitor will be responsible for reviewing:

- Interim side effect/toxicity data for this trial and proposing corrective actions when the side effects for any treatment are unexpectedly severe. Nonetheless, the PI and study team have primary responsibility for monitoring toxicity. Corrective actions by the medical monitor may include:
 - modifying the treatment
 - early suspension of the trial
 - limiting the participation in the trial to a subset of the original subject population
- Interim analyses of outcome data prepared by the statisticians, with recommendations for change in the study status on the basis of these analyses. These changes may include:
 - early termination of accrual
 - release of results consistent with any sequential stopping rules used in the design of the study
 - increases to the accrual goal
 - major changes to the eligibility criteria for the trial
- The impact of independent scientific investigations (other trials) on the trial being monitored, as well as recommending changes based on those external results.
- Requests for data from sponsoring organizations or any other party. This includes requests for preliminary data for planning ancillary studies. These responsibilities end after the unblinding of the trial, with the medical monitor not involved in further review of the trial. However, the research team may consult the medical monitor on other issues thereafter, such as appropriate action for late toxicities.

The medical monitor will have face-to-face meetings with the research team twice per year. More frequent phone conferences will be held if deemed necessary, for an evaluation of adverse events.

ClinicalTrials.gov

The trial is registered on the ClinicalTrials.gov website. ClinicalTrials.gov Identifier:

NCT03261271

References

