Primary and Secondary Aims	
1. Test the impact of weight management on obesity-driven prostate cancer biomarkers taken at baseline, 1 week prior to surgery, and 6 months after surgery.2. Evaluate how weight management affects weight loss, body composition, and weight maintenance in overweight men with localized prostate cancer.3. Test the impact of weight management on QoL in prostate cancer survivors.
Statistics	A two-sample t-test will be used to assess the differences in outcomes between the two groups. The significance of within-group differences will be assessed using a paired t-test.

Table of Contents

Protocol Synopsis	2
Table of Contents	3
Schema	4
Abstract	5
Background and Significance	6-9
Preliminary Data	9
Aims and Hypothesis	9-10
Research Design and Methods	11-18
Data Collection	18-22
Statistical Analysis	22
Protection of Human Subjects	23-25
Benefits to Patients	25
Adverse Event Reporting	25
Safety Monitoring	25-26
References	27-31

Schema of Intervention: Weight management Aimed to Reduce Risk and Improve Outcomes from Radical Prostatectomy, WARRIOR

Abstract:

Men who are overweight at the time of prostate cancer surgery are more likely to have their cancer come back than healthy weight men. Healthy weight men also tend to live longer after prostate cancer surgery than overweight men. Fat tissue makes signals that allow cancer to grow and extend beyond the prostate gland, and overweight men have a higher level of these signals. One of the signals is a harmful immune cell that impairs the ability of the immune system to keep cancer in check. Prostate cancer patients with higher levels of these immune cells are more likely to die sooner than men with lower levels of the immune cells. Also, these harmful immune cells use up a nutrient that is needed to produce a signal for penile erection, a common problem after prostate cancer surgery. We think that helping men lose weight before their prostate cancer is removed will help weaken prostate cancer before surgery and prevent it from establishing new tumors in other places in the body. Therefore, weight loss may help prevent the spread of cancer and improve prostate cancer survival and quality of life.

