Immune suppressive factors lead to PCa recurrence and death. Myeloid-derived suppressor cells (MDSCs) play a crucial role in cancer-induced immune dysfunction by establishing an immune suppressive environment in prostate tumors.⁴ High levels of MDSCs are associated with a shorter survival in PCa patients.⁵ Furthermore, MDSC frequencies correlate with PCa stage.⁶ Prostate tumors express high concentrations of pro-inflammatory cytokines and MDSCs,⁵ which lead to immunosuppression thereby making it more difficult for the immune system to keep cancer in check.⁷ Interestingly, the monocytic MDSC subtype is predominant in the blood of patients prior to RP when the tumor is present, but the frequency of the monocytic MDSC subtype decreases after the tumor is removed.⁸ Furthermore, our team routinely measures MDSCs in patients before and after cancer surgery.⁹ Our pilot data show reduced total and monocytic MDSCs in the weight management intervention ($P = 0.09$; $P = 0.17$, respectively), and the changes in these cell frequencies were different compared to the prospective controls before RP ($P = 0.06$; $P = 0.17$, respectively). We also found that the monocytic MDSC frequencies decrease substantially after RP, but total MDSCs and Tregs do not change with the removal of the tumor. These observations support that the intervention timing is ideal to evaluate the effects of weight loss on tumor-mediated immunosuppressive mechanisms in the peri-operative time frame.

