maintenance after PCa surgery on obesity-driven PCa biomarkers. Forty men with stage T1 or T2 PCa scheduled to undergo RP will be randomized to receive a weight management program (intervention; n = 20) or standardized education materials (control; n = 20). Our pilot work has established that men awaiting RP are very motivated and embrace the pre-surgical intervention as a means to cope with anxiety by improving their health. We employ a weight loss intervention that emphasizes competition, autonomy, technology, cost savings, and male-specific barriers to change—factors that prior studies have found to be important to successful weight loss interventions among men. We also examine critical QoL factors that could affect the feasibility of the intervention in future trials and clinical practice. Our hypotheses and specific aims are:

1. *To test the impact of weight management on obesity-driven PCa biomarkers taken at baseline, 1 week prior to surgery, surgery and 6 months after surgery.

Hypothesis 1.1: Immune suppressive factors will respond to the intervention with reduced total MDSC (Lin- CD11b+ CD33+) and monocytic MDSC (Lin- CD11b+ CD33+ CD14+ CD15-) counts compared to baseline values and to the control group. **Primary Objective**

Hypothesis 1.2: Participants in the intervention group will have a more favorable chemokine, adipokine, and cytokine profile than the participants in the control group.

2. To evaluate how weight management affects weight loss, body composition, and weight maintenance in overweight and obese men with localized PCa.

Hypothesis 2.1: The intervention will lead to significant weight reduction compared to the control group from baseline to 1 week prior to surgery.

Hypothesis 2.2: The intervention will reduce body fat and maintain lean body mass as measured by Dual Energy X-Ray Absorptiometry (iDXA) scans from baseline to 1 week prior to surgery.

Hypothesis 2.3: The intervention will lead to weight maintenance (<3% regain) 6 months after RP.

3. To test the impact of weight management on QoL in PCa survivors.

Hypothesis 3.1: The intervention will report better urinary function and lower urinary bother compared to control 6 months after RP as measured by the Expanded PCa Index Composite (EPIC) Instrument-26.

Hypothesis 3.2: The intervention will improve sexual function and QoL 6 months after RP as measured by the EPIC-26.

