Immune Biomarkers		X	X	X
Inflammation Biomarkers		X	X	X
Cardiometabolic Markers		X	X	X
Microbiome		X	X	X

Justification of sample size: We powered this study for aims 1 and 2, but aim 3 and 4 are exploratory. The power calculations used effect sizes and standard deviations from our pilot study (ClinicalTrials.gov: NCT02252484). The primary objective is to reduce obesity-driven biomarkers (MDSCs) of PCa recurrence and death. Our pilot study showed that weight loss of 1.2 pounds/week corresponds to a decrease in MDSC by 1.4 counts/week. Group sample sizes of 17 and 17 achieve over 80% power to detect a change in MDSC of 1.2 per week between the intervention and control groups with standard deviations of 1.6 and 0.3 (obtained from our pilot study) with a significance level of 0.05 using a two-sided, two-sample t-test. Secondary objective: Thirty-four participants will detect weight change as low as 0.5 kg/week between the intervention and control groups using the standard deviations of 0.6 and 0.1, from our pilot study. Weight maintenance will also be examined. If the intervention maintains their weight loss within 3%, 17 patients will give power over 80% to detect equivalency in the intervention group assuming the moderate correlation of 0.4 using paired t-tests. Tertiary objectives to assess the impact of weight loss on QoL using the EPIC-26 tool are exploratory. The results will be used to calculate effect sizes for a definitive, large multi-site clinical trial.

Statistical Analysis Prior to initiating outcome analyses, we will summarize the baseline characteristics of the data. Tests will be considered significant if the *P*-value is less than 0.045 for the final analysis. Our data may include missing observations related to either attrition or nonresponse and this type of missing data can reasonably be assumed to be random. We will run an intention to treat analysis for all outcomes. Comparisons will be carried out separately for the weight loss phase (enrollment to 1 week prior to surgery) and the weight maintenance phase (1 week prior to surgery to 6 months after surgery). Since patients will be on the pre-surgical phase for varying durations of time, we will assess the rate of weight loss between the two groups. A two-sample t-test will be used to assess the differences in outcomes between the two groups. The significance of within-group differences will be assessed using a paired t-test.

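### Prostatectomy itself lowers monocytic MDSC and impairs erection, so within-arm change across surgery cannot show a programme effect, and the plan does not say that the control comparison decides

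*Combined protocol and SAP*

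**What the plan says.** **Hypotheses.** Under Aims and Hypothesis, Hypothesis 1.1 is marked as the primary objective. It expects reduced total and monocytic MDSC "counts compared to baseline values and to the control group". The parent aim has its biomarkers "taken at baseline, 1 week prior to surgery, surgery and 6 months after surgery". Hypotheses 2.1 and 2.2 are confined to the interval from baseline to 1 week before surgery; Hypothesis 1.1 is not. Hypothesis 3.1 predicts "better urinary function and lower urinary bother compared to control 6 months after RP". Hypothesis 3.2 reads "The intervention will improve sexual function and QoL 6 months after RP as measured by the EPIC-26" and names no comparator.

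**What surgery does.** The Background paragraph on immune suppressive factors reports from the team's own observations that "monocytic MDSC frequencies decrease substantially after RP, but total MDSCs and Tregs do not change with the removal of the tumor". The Abstract refers to a nutrient needed "to produce a signal for penile erection, a common problem after prostate cancer surgery".

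**Analysis.** The Statistical Analysis section makes comparisons separately for a weight-loss phase (enrolment to 1 week before surgery) and a maintenance phase (1 week before to 6 months after surgery). A two-sample t-test compares the groups, and "The significance of within-group differences will be assessed using a paired t-test". The final significance level is 0.045. The sample size justification rests the MDSC power on the between-group comparison and declares Aim 3 exploratory.

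**The concern.** The operation falls between the second and third visits in both arms. Any within-arm change over that interval mixes the surgical effect with whatever the programme does, and a paired test in the intervention arm cannot separate them.

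For monocytic MDSC, surgery pushes in the direction that Hypothesis 1.1 calls a response, so tumour removal could be reported as a benefit of weight management. For sexual function, surgery pushes the other way. If improvement is read against a man's own earlier score, a programme that protects function could look as if it had failed.

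Only the control arm, which has the same operation, removes the shared effect. The plan collects and tests that comparison, but nowhere says that it decides the post-surgery conclusion or that the paired tests in that phase are descriptive.

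**Working it through.** **1. The plan's own power figure.** Inputs from the sample size justification: 17 per arm, difference 1.2 counts/week, SDs 1.6 and 0.3, two-sided alpha 0.05.

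- Standard error = √(1.6²/17 + 0.3²/17) = 0.395; 1.2/0.395 = 3.04; Welch degrees of freedom 17.1.
- Noncentral t power is 81.7% (Welch) or 83.8% (pooled SD 1.151), against the stated figure of over 80%.
- At alpha 0.045 the values are 80.3% and 82.6%.
- The inflation also reproduces: 34/0.9 = 37.8, rounded up to 38; 38/0.95 = 40.

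The sample size is not at fault.

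**2. Paired test across surgery, no programme effect.** Let d be the fall caused by surgery alone, in SDs of within-man change. The documents give no value, so d is an assumption and a range is shown. With n = 17 and alpha 0.045, the critical t on 16 df is 2.175 and the noncentrality is d√17. The last column is a 100,000-run simulation with the same shift in both arms.

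| Assumed d | d√17 | Paired test significant | Between-group test significant |
|---|---|---|---|
| 0 | 0 | 4.5% | 4.5% |
| 0.25 | 1.03 | 15% | 4.4% |
| 0.5 | 2.06 | 47% | 4.4% |
| 0.75 | 3.09 | 81% | 4.5% |
| 1.0 | 4.12 | 97% | 4.5% |

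**3. If Hypothesis 1.1 needs both comparisons.** A false success then also requires a significant between-group difference favouring the programme. With no programme effect its probability is at most 0.045/2 = 2.25%, whatever surgery does to the paired test.

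**4. Sexual function, illustration only.** Assume surgery shifts the score by −1.0 SD and the programme truly adds +0.5 SD, a net change of −0.5 SD. With 17 per arm, the paired test shows significant worsening in 47% of trials and significant improvement in under 0.1%. The between-group test shows benefit in 28%. With −1.0 and +0.8 SD the three figures are 11%, 0.2% and 60%. With −1.5 and +0.8 SD they are 76%, 0% and 60%. No size for either effect is in the documents. The illustration shows only that the two tests answer different questions.

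**The case against.** The case for leaving the plan alone is substantial.

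- **Only one of the two primary markers is affected.** A reader might infer that tumour removal can satisfy the within-arm part of Hypothesis 1.1 by itself. The documents do not support that: the sentence reporting the monocytic fall also says that total MDSC do not change, and the hypothesis names both markers.
- **The comparisons are joined by a conjunction.** On the natural reading, a fall shared by both arms fails the comparison with control, and the 2.25% cap applies. This stands as a reading, but no rule says that both are required, and a paired P-value below 0.045 counts as significant under the plan either way.
- **No baseline-to-6-month window is defined.** Under the two stated phases, the comparison with baseline is tested before surgery, where it is clean. This stands, but the maintenance phase still applies a paired test across the operation, starting from the pre-surgical value, and Hypothesis 1.1 sets no time limit.
- **Hypothesis 3.2 is silent, not wrong.** A reader might infer that it is to be judged against each man's own baseline and is likely to fail. The text does not say that. The general two-sample test also applies to it, and Aim 3 is exploratory. What remains is an inconsistency with Hypothesis 3.1. It matters because the results are meant to supply effect sizes for a larger trial.
- **The size is assumed.** This is true. At 0.5 SD a spurious fall is about as likely as not, so it should not be called expected. Yet even 0.25 SD more than triples the nominal 4.5%.

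**Conclusion.** The point holds within limits. A within-arm fall in monocytic MDSC across prostatectomy is not evidence of a programme effect, and the plan leaves room to treat it as such. With no programme effect, the paired test is significant in 15% to 97% of trials for assumed surgical shifts of 0.25 to 1.0 SD, against a nominal 4.5%, while the between-group test holds its level. These figures rest on 17 men per arm, normally distributed changes and an equal surgical effect in both arms.

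Total MDSC, the pre-surgery phase and the powered between-group comparison are not affected. If both comparisons in Hypothesis 1.1 must succeed, a false success is at most about 2.2%; the plan should say whether they must. For Hypothesis 3.2 the defect is a missing comparator in an exploratory aim. The correction is worth making because it is cheap and the control arm needed for it is already randomised.

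**What to change.** For MDSC and EPIC-26 outcomes only:

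1. In Hypothesis 1.1 and the Statistical Analysis section, state that any conclusion about programme effect at 6 months after surgery rests on the randomised comparison of intervention with control, and that paired within-arm change across surgery is descriptive. Preferably compare the 6-month values adjusted for the pre-randomisation baseline. Change scores over the maintenance phase start from a value that the programme may already have altered, so they may not isolate its effect cleanly.
2. Keep the paired tests for the weight-loss phase.
3. Reword Hypothesis 3.2 to predict better sexual function and QoL than control at 6 months, matching Hypothesis 3.1.

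The restriction should not extend to every outcome. Hypothesis 2.3 has a planned paired weight-maintenance analysis in the intervention arm, and Hypothesis 4.2 asks which microbial populations surgery alters. Both need within-arm change across surgery and should stay as they are.

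The cost is wording: two hypotheses and the analysis text. No new data, visits or participants are needed, and the sample size is unchanged. The sponsor gives up within-arm P-values across surgery as evidence for these outcomes.

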Men who are overweight at the time of radical prostatectomy (RP) are more likely to have recurrence and die from prostate cancer (PCa) than healthy weight men.^{50–52} Men who gain additional weight after RP are also at increased risk of recurrence.^{51–53} Obesity exacerbates immune suppressive factors associated with PCa progression^{28, 31} and death.⁵ Conversely, weight loss may reduce immune suppression at the site of the tumor and help prevent the spread of cancer outside the prostate gland. Weight loss *prior* to RP could be the optimal time to influence PCa prognosis. Research conducted in our laboratory found that a weight loss intervention administered prior to surgery led to 6 kg of weight loss (95% CI, 3–8 kg; $P < 0.001$) and 4 kg of fat loss (95% CI, 2–6 kg; $P < 0.001$) from baseline to surgery (mean = 6.6 weeks) among 15 overweight men. Moreover, the intervention reduced immune suppressive myeloid derived suppressor cells (MDSCs) in our weight management arm before RP compared to the prospective control arm. It remains unclear how weight loss affects other obesity-driven biomarkers of PCa progression, urinary outcomes, and sexual outcomes which are all important for better survival and quality of life (QoL). There is a critical need to examine the effects of weight loss on immune profiles, inflammation response, and QoL in order to determine whether large-scale trials of weight loss to enhance PCa survivorship are justified to disrupt the obesity-cancer link.

Our long term goal is to improve PCa prognosis, survival, and QoL after RP. The primary objective of this application is to assess the impact of weight loss *before* and weight

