History of radiation therapy for cancer treatment	"
Taking active cancer treatment	"
Undergoing salvage therapy	"
Castration-resistant PCa	Avoid harm to patients with a poor prognosis or altering their course of treatment
Evidence of metastasis	"
Evidence of biochemical recurrence	"
High risk medical condition (e.g. kidney disease, uncontrolled diabetes, etc.)	"

*If patients do not own a compatible device the study team will loan a device to be returned at the end of the study

AIM 2: Evaluate how weight management affects weight loss, body composition, and weight maintenance in overweight and obese men with localized PCa.

Study Intervention components: The cornerstone of weight management for overweight and obese adults is a comprehensive program, which includes a reduced calorie diet along with exercise and behavior change components.⁵⁴ Our weight management program is designed to help participants lose $\geq 5\%$ of their body weight before their RP and to help them maintain that weight loss after their surgery. This goal can be challenging, yet we find that men scheduled for RP are highly motivated. However, the motivation wanes after surgery. Although our four-component intervention may at first glance seem complicated, our approach is actually very simple as demonstrated by the 90% retention in our pilot study.

Behavior therapy/Coaching: Face-to-face coaching sessions are used to discuss progress, overcome obstacles, make adjustments to the diet and exercise regimen, and learn diet and exercise strategies for cancer survivorship. Before the surgery, the one-on-one coaching sessions occur weekly. After the surgery, 4 coaching sessions are given every 6 weeks in a setting with other study participants, spouses/caregivers, and the coach. Coaches are trained as health educators with credentials as either personal trainers or dietitians working under the supervision of [name] who is also board-certified in oncology nutrition and certified as a personal trainer. Patients and coaches also connect within the app for real-time monitoring and reinforcement. The dashboard on the app shows body weight to reinforce self-efficacy and accountability.

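### Meeting Hypothesis 2.3 (<3% regain) would not by itself show maintained weight loss: no reference weight or prior loss is stated, and no enrollment-to-6-month comparison is planned

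*Combined protocol and SAP*

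**What the plan says.** - **Aims and Hypothesis, Aim 2:** "Hypothesis 2.3: The intervention will lead to weight maintenance (<3% regain) 6 months after RP". No reference weight, denominator, minimum prior loss or comparator is given. The preceding hypothesis on loss does name a comparator and a period: "Hypothesis 2.1: The intervention will lead to significant weight reduction compared to the control group from baseline to 1 week prior to surgery".
- **Aim 2, Study Intervention components:** the program is meant to produce a loss of at least 5% before surgery and then "to help them maintain that weight loss after their surgery".
- **Statistical Analysis:** comparisons are made separately for enrollment to 1 week before surgery and for "the weight maintenance phase (1 week prior to surgery to 6 months after surgery". Between-group differences use a two-sample t-test, within-group differences a paired t-test, and all outcomes are analyzed by intention to treat.
- **Justification of sample size:** "If the intervention maintains their weight loss within 3%, 17 patients will give power over 80% to detect equivalency in the intervention group". The calculation is for a paired test and takes the correlation between the two weights as 0.4. No standard deviation is given for this statement.
- **Table 3:** body weight is scheduled at baseline, before surgery and after surgery. The Control group section provides the same data collection in controls.

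**The concern.** The goal in Aim 2 concerns weight that has been lost and is then kept off. The hypothesis meant to capture it measures only regain, and the analysis starts the clock at the pre-surgery visit. Enrollment weight and the amount lost do not enter. Because the analysis is by intention to treat, men who lost nothing stay in, and for them a stable weight is a favorable result.

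The planned between-arm comparison of the maintenance phase does not repair this. Its starting weight is measured after randomization and is itself changed by the intervention, so the arm that lost more has more to regain.

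At stake is the conclusion the trial would draw at 6 months. A statement that weight loss was maintained could rest on a test that would give the same answer had little weight been lost.

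**Working it through.** **1. The plan's own figure.** The claim is over 80% power with 17 men, a 3% limit and correlation 0.4. It can be neither confirmed nor refuted, because no SD is stated. With SD of change = SD × √(2 × (1 − 0.4)), two one-sided paired tests and a true change of zero, 80% power requires an SD of change of at most about 4.0% of body weight (0.05 or 0.045 per side), or 3.5% to 3.6% (0.025 or 0.0225 per side). Prior loss appears nowhere in this calculation. An arm that lost nothing and truly stays level has the same chance of being declared equivalent as one that lost 6 kg and stays level.

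**2. When full regain passes.** Take 3% of pre-surgery weight, the reading that the phase definition suggests. Let L be the loss as a fraction of enrollment weight. Full regain is L/(1 − L) of pre-surgery weight, and this is below 0.03 only if L < 1 − 1/1.03 = 2.91%. At just 3% regain, the final weight is (1 − L) × 1.03 of enrollment weight.

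| Loss before surgery | Full regain, % of pre-surgery weight | Below 3%? | Net change from enrollment at 3% regain |
|---|---|---|---|
| 0% | 0 (nothing to regain) | yes | +3.0% |
| 2% | 2.04% | yes | +0.94% |
| 3% | 3.09% | no | −0.09% |
| 5% (program goal) | 5.26% | no | −2.15% |
| 5.4% (pilot) | 5.71% | no | −2.56% |

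At a 5% loss, 0.03 × 0.95/0.05 = 57% of the loss can return within the limit.

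**3. Can a loss below 2.91% occur?** The documents give two pilot rates:
- Justification of sample size: "Our pilot study showed that weight loss of 1.2 pounds/week corresponds to a decrease in MDSC by 1.4 counts/week". 1.2 lb × 0.4536 = 0.544 kg/week.
- Aims and Hypothesis: 6 kg "from baseline to surgery (mean = 6.6 weeks) among 15 overweight men". 6/6.6 = 0.909 kg/week.

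The Synopsis accepts a 4-week wait, and the pre-surgery visit is 1 week before surgery, so about 3 weeks of loss may be all that is observed. Assume 95 kg (pilot mean BMI 30, assumed height 1.78 m: 30 × 1.78² = 95).
- At 0.544 kg/week for 3 weeks, the loss is 1.63 kg. The limit is 0.03 × 93.4 = 2.80 kg, so he could end 1.17 kg above enrollment. Over BMI 25 to 35 and height 1.70 to 1.85 m (72 to 120 kg) the range is +0.5 to +1.9 kg.
- At 0.909 kg/week for 3 weeks, the loss is 2.73 kg. The limit is 0.03 × 92.3 = 2.77 kg, so he could end 0.04 kg above enrollment. The range over the same weights is −0.6 to +0.8 kg.
- At 0.544 kg/week for 4 weeks, the loss is 2.0% to 2.6% for 111 to 85 kg, so full regain passes. At 6.6 weeks it is 3.2% to 4.2%, so full regain fails.

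**4. The between-arm maintenance comparison (illustration).** A control man stays at 95 kg. An intervention man goes from 95 to 89 kg, then to 91 kg.
- Pre-surgery to 6 months: control 0 kg, intervention +2 kg (2/89 = 2.2%). Control looks better by 2 kg.
- Enrollment to 6 months: control 0 kg, intervention −4 kg (4/95 = 4.2%). Intervention is better by 4 kg.

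**5. The other reading of the 3%.** The sample-size wording could mean 3% of the weight lost. For a 6 kg loss that is 0.18 kg, close to the stated scale accuracy of ±0.1 kg. Full regain would then always fail, and a man with no loss would have no defined value.

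**The case against.** Several points on the other side are sound.

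- **Loss is tested elsewhere.** Hypothesis 2.1 tests loss against control, so 2.3 can be read as its sequel. This stands in part. However, 2.1 stops before surgery, 2.3 is not made conditional on it, and the two together still give no net change from enrollment.
- **Starting at surgery has a rationale.** Aims and Hypothesis notes that weight gain after surgery carries its own recurrence risk. Regain from the pre-surgery weight is therefore worth analyzing, and the equivalence test should stay.
- **The test is for the group.** A reader might infer that each man is scored a success or failure. The documents define no such rule; they describe a paired equivalence test in the intervention arm. The confidence interval, not only the mean, must then lie inside 3%. With an SD of change of 4.0% and n = 17, its half-width is 1.746 × 4.0/√17 = 1.7%, so the observed mean regain would have to be below about 1.3%. For an arm's mean loss, 2.91% is therefore an upper bound. A stable arm with no prior loss is unaffected.
- **The pre-surgery reference is inferred.** It comes from the phase definition; Hypothesis 2.3 does not state it. That ambiguity is part of the finding.
- **A between-group test exists.** A reader might infer that there is no control comparison at all. The Statistical Analysis section plans one for each phase; the difficulty is its post-randomization starting point.

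**Conclusion.** The point holds as a gap in definition and analysis. As written, Hypothesis 2.3 can be met by an intervention arm with little or no pre-surgery loss and a stable weight, and no specified analysis asks whether men are lighter at 6 months than at enrollment. Meeting it would not by itself show that the Aim 2 goal was reached.

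A reader might infer that any man who regains everything meets the criterion. The documents do not support that. On the pre-surgery-weight reading it is true only for losses below 2.91% of enrollment weight, and full regain fails at the 5% goal and at the 5.4% pilot loss. Nor do they support a fixed excess over enrollment for short-wait men: at 95 kg it is 1.17 kg at one pilot rate and 0.04 kg at the other. It would also go too far to say that the criterion cannot separate the arms. What can be said is that it does not measure retained loss, and that the maintenance-phase comparison may favor control.

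These figures assume 3% of pre-surgery weight, the stated body sizes and a constant weekly rate. The central finding needs only the absence of a prior-loss requirement and of an enrollment-anchored comparison. This is one hypothesis under a secondary aim; the primary objective is untouched.

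**What to change.** - Add percent change in weight from enrollment to 6 months after surgery, compared between arms by intention to treat, as the analysis that supports any claim of maintained weight loss. It starts from a pre-randomization weight and so keeps the randomized comparison intact.
- Keep the 3% paired equivalence analysis in the intervention arm. State that its reference and denominator are the pre-surgery weight, or otherwise reconcile Hypothesis 2.3 with the sample-size wording.
- Report the equivalence result together with the loss achieved before surgery.

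I would not replace it with a responder rule of at least 5% below enrollment weight. At 0.544 kg/week a 95 kg man needs 4.75/0.544 = 8.7 weeks to lose 5%, so such a rule would largely track the length of the surgical wait.

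The cost is one derived variable and one extra analysis, using weights already scheduled in both arms. The maintenance result may look less favorable, and the existing power statement would cover only the equivalence test, not the added comparison.
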